4. STUDY DESIGN

4.1. Overall Design

This is an open-label, single-dose study to assess the safety, tolerability, and PK of GSK3810109 administered SC with rHuPH20 or IV in healthy adult participants.

This study will comprise 3 parts:

In Part 1, approximately 8 participants will receive a single 20 mg/kg SC dose of GSK3810109 co-administered with rHuPH20 at dose of 2000 U/mL or ~28,000 U for a 70 kg participant. The participants will be admitted in the clinic on Day –1 and the study product will be administered on Day 1. The participants will remain in the clinic for approximately 8 hours for study-related procedures after study product administration and will be followed up for 24 weeks.

Safety laboratory samples will be collected throughout the study as per the SoA. The primary endpoint of ISR will be evaluated at specified time points up to Day 7; study participants will keep a diary of ISRs for 14 days after study product administration. Symptoms, maximum intensities, and durations will be reported through end of study to characterize presentation and resolution of local ISRs.

Safety review decisions and the status of the enrollment process will be shared with the Safety Review Team (SRT) in regular intervals and discussed during the monthly SRT meetings.

In Part 2, approximately 8 participants will receive a single 60 mg/kg IV dose of GSK3810109. A sentinel cohort of 2 participants will be used to mitigate the risk of unexpected AEs prior to dosing of the remaining 6 participants, who will be dosed in sequential cohorts of 2 participants each.

The sentinel cohort of these 2 participants will be admitted to the clinic on Day –1. The study product will be administered on Day 1 and participants will remain in the clinic and be monitored for 7 days after study product administration. The participants will be discharged from the clinic on Day 8 and will be followed up for 24 weeks.

Following Day 10 visit, core SRT will review the safety data (safety laboratory data, ECG, and AEs) from the sentinel cohort and may recommend continuation of the study where the next cohort of 2 participants will be dosed.

[figure not shown]
The second cohort of 2 participants will be admitted to the clinic on Day –1. The study product will be administered on Day 1 and participants will remain in the clinic and be monitored for 7 days after study product administration. The participants will be discharged from the clinic on Day 8 and will be followed up for 24 weeks. A review of at least AE data from this cohort will be conducted after a minimum of 4 days following infusion of GSK3810109 and the core SRT may recommend continuation of the study where the next cohort of 2 participants will be dosed.

The third cohort of 2 participants will be admitted to the clinic on Day –1. The study product will be administered on Day 1 and participants will remain in the clinic and be monitored for 7 days after study product administration. The participants will be discharged from the clinic on Day 8 and will be followed up for 24 weeks. A review of at least AE data from this cohort will be conducted after a minimum of 4 days following infusion of GSK3810109 and the core SRT may recommend continuation of the study into the fourth cohort of 2 participants.

The fourth cohort of 2 participants will be admitted to the clinic on Day –1. The study product will be administered on Day 1 and participants will remain in the clinic and be monitored for 7 days after study product administration. The participants will be discharged from the clinic on Day 8 and will be followed up for 24 weeks.

Safety laboratory samples will be collected throughout the study as per the SoA.

CCI

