The third cohort of 2 participants will be admitted to the clinic on Day –1. The study product will be administered on Day 1 and participants will remain in the clinic and be monitored for 7 days after study product administration. The participants will be discharged from the clinic on Day 8 and will be followed up for 24 weeks. A review of at least AE data from this cohort will be conducted after a minimum of 4 days following infusion of GSK3810109 and the core SRT may recommend continuation of the study into the fourth cohort of 2 participants.

The fourth cohort of 2 participants will be admitted to the clinic on Day –1. The study product will be administered on Day 1 and participants will remain in the clinic and be monitored for 7 days after study product administration. The participants will be discharged from the clinic on Day 8 and will be followed up for 24 weeks.

Safety laboratory samples will be collected throughout the study as per the SoA.

CCI

An initial cohort of 2 participants will be used to mitigate the risk of unexpected AEs prior to dosing of the remaining 6 participants.

In the first cohort, 2 participants will be admitted in the clinic on Day –1 and the study product will be administered on Day 1. The participants will remain in the clinic and be monitored for 3 days after study product administration. The participants will be discharged from the clinic on Day 4 and will be followed up for 24 weeks. Following discharge, core SRT will review at least AE data and may recommend continuation of the study where the next cohort of 6 participants will be dosed.

The second cohort of 6 participants will be admitted to the clinic on Day –1. The study product will be administered on Day 1 and participants will remain in the clinic and be monitored for 3 days after study product administration. The participants will be discharged from the clinic on Day 4 and will be followed up for 24 weeks.

Safety laboratory samples will be collected throughout the study as per the SoA. The primary endpoint of ISR will be evaluated at specified time points up to Day 7; study participants will keep a diary of ISRs for 14 days after study product administration.

Symptoms, maximum intensities, and durations will be reported through end of study to characterize presentation and resolution of local ISRs.

Note: Results of Part 3 will be reported separately from Part 1 and Part 2.

Interim Analysis

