7. DISCONTINUATION OF STUDY INTERVENTION AND PARTICIPANT DISCONTINUATION/WITHDRAWAL

7.1. Discontinuation of Study Intervention

Emerging safety data will be reviewed in-stream as the study progresses and the following criteria will result in a study pause. A full safety review will be conducted, and the findings and recommendations presented to ViiV Safety and Labelling Committee (VSLC) for endorsement:

- Any SAE, regardless of its severity, that is considered be clinically significant and reasonably attributable to dosing with GSK3810109, in the opinion of the investigator and sponsor.
- Acute allergic reaction or CRS (Division of AIDS [DAIDS] criteria Grade 3 to 4) reasonably attributable to dosing with GSK3810109, in the opinion of the investigator and sponsor.
- Any AE of Grade 4 intensity assessed as related to GSK3810109, as reported by the investigator.
- Any participant meeting liver chemistry stopping criteria (see Section [7.2](#))
- Any participant meeting QTcF stopping criteria (see Section [7.3](#))
- If 2 participants in any discrete part of the study (Part 1, Part 2, or Part 3) experience an AE of Grade 3 intensity (excluding ISRs) assessed as related by the investigator.
- If 2 or more injections/infusions administered in any discrete part of the study (Part 1, Part 2, or Part 3) are followed by an ISR of at least Grade 3 in severity.

Note: Grade 3 ISRs that are based on the size of erythema or induration alone will not be considered as a pausing criterion. However, any Grade 3 ISR of erythema or induration due to ulceration, secondary infection, phlebitis, sterile abscess, drainage, or symptoms causing inability to perform usual social and functional activities (as per DAIDS) will be included as a pausing criterion.

Relevant reporting and discussion with the Medical Monitor, relevant study team personnel, and the institutional review board (IRB)/independent ethics committee (IEC) will take place before resumption of dosing. Every effort will be made to take a blood sample at the time of the AE for PK analysis.

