7.3. QTcF Stopping Criteria

If a participant meets the below mentioned QTcF stopping criteria, the study will pause to conduct an evaluation of the relevant safety data. The findings and recommendations on dosing resumption will be presented to VSLC for endorsement.

QTcF Stopping Criteria:

- QTcF > 480 msec,
- Change from baseline: QTcF > 60 msec

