10.1.5. Committees Structure

An SRT for GSK3810109 reviews emerging and cumulative data for GSK3810109 on a monthly basis. For Part 1, safety review decisions and the status of the enrollment process will be shared with an SRT at regular intervals and discussed during the monthly SRT meetings.

For Part 2, a core SRT for Study 217901 study will review data for both sentinel and non-sentinel participants of the study. For Part 3, the core SRT will review data for the 2 participants in the first cohort before enrolling the next 6 participants. The core SRT is composed of safety lead, medical monitors, and project biostatistician.

The SRT will make recommendations to the VSLC regarding safety findings, including study pause, modification, and termination. The VSLC is chaired by the ViiV Chief Medical Officer and will have the final decision on study modifications, including termination. Details regarding the VSLC membership and function are included within the VSLC Charter.

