| 
• An unsolicited AE is an AE that was not solicited using a participant diary and that is communicated by a participant who has signed the informed consent. Unsolicited AEs include serious and non-serious AEs.• Potential unsolicited AEs may be medically attended (i.e., symptoms or illnesses requiring a hospitalization, emergency room visit, or visit to/by a healthcare provider). The participants will be instructed to contact the site as soon as possible to report medically attended event(s), as well as any events that, though not medically attended, are of participant concern. Detailed information about reported unsolicited AEs will be collected by qualified site personnel and documented in the participant's records.• Unsolicited AEs that are not medically attended nor perceived as a concern by the participant will be collected during an interview with the participants and by review of available medical records at the next visit.• Solicited AEs are predefined local at the injection site and systemic events for which the participant is specifically questioned, and which are noted by the participant in their diary. |

Events Meeting the AE Definition

- Any abnormal laboratory test results (hematology, clinical chemistry, or urinalysis) or other safety assessments (e.g., ECG, radiological scans, vital signs measurements), including those that worsen from baseline, considered clinically significant in the medical and scientific judgment of the investigator (i.e., not related to progression of underlying disease).
- Exacerbation of a chronic or intermittent pre-existing condition including either an increase in frequency and/or intensity of the condition.
- New condition detected or diagnosed after study intervention administration even though it may have been present before the start of the study.
- Signs, symptoms, or the clinical sequelae of a suspected intervention- intervention interaction.
- Signs, symptoms, or the clinical sequelae of a suspected overdose of either study intervention or a concomitant medication. Overdose per se will not be reported as an AE/SAE unless it is an intentional overdose taken with possible suicidal/self-harming intent. Such overdoses should be reported regardless of sequelae.

Events NOT Meeting the AE Definition

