#### ECG:

ECG data summaries will be reported by study part. Change from baseline will be summarized by timepoint for ECG values. As triplicate measurements of ECG will be taken for all postdose timepoints, average of these assessments will be used for summary tables. For ECG values, the frequency in different categories of maximum post-baseline QTcF values, including maximum change from baseline in QTcF, will be provided. Categories for maximum post-baseline QTcF

values will include no change or decrease to  $\leq 450$  msec, increase to  $>450$  to  $\leq 480$ , increase to  $>480$  to  $\leq 500$  msec, or increase to  $>500$  msec and categories for maximum change from baseline in QTcF will include increase of  $\leq 30$  msec, increase of  $>30$  to  $\leq 60$  msec, or increase of  $>60$  msec. A separate summary table of ECG findings will be created. All ECG values and all ECG findings for participants with an abnormal finding will be listed separately. ECG values will include measurements of heart rate, PR, QRS, QT, and QTcF intervals.

Vital Signs:

Vital signs data summaries will be reported by study part. Vital sign assessments will include temperature, systolic and diastolic blood pressure, respiratory rate, and pulse. Change from baseline over time in vital signs and SPO2 will be summarized with descriptive statistics by timepoint. All vital signs data along with SP02 will be listed.

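### Reviews that release the third and fourth Part 2 pairs and the six-person Part 3 cohort can rest on AE data alone, although laboratory and ECG results are already scheduled by then

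*Protocol*

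**What the plan says.** The protocol sets two standards for the reviews between cohorts.

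- **Part 2, sentinel pair (Sections 1.1 and 4.1).** After the Day 10 visit, "core SRT will review the safety data (safety laboratory data, ECG, and AEs) from the sentinel cohort".
- **Part 2, second and third pairs (Sections 1.1 and 4.1).** "A review of at least AE data from this cohort will be conducted after a minimum of 4 days following infusion of GSK3810109". These reviews release the third and fourth pairs.
- **Part 3, first cohort (Section 1.1).** After discharge on Day 4, "core SRT will review at least AE data and may recommend continuation of the study where the next cohort of 6 participants will be dosed".
- **Committees Structure (Section 10.1.5).** For Part 2 the core SRT "will review data for both sentinel and non-sentinel participants of the study". For Part 3 it reviews data on the first two participants. Neither sentence states the type of data or whether they must be complete.

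Alongside these reviews, Section 7.1 provides that "Emerging safety data will be reviewed in-stream as the study progresses and the following criteria will result in a study pause". Two of its seven criteria depend on laboratory or ECG results: liver chemistry (Section 7.2, ALT at or above 3 x ULN) and QTcF (Section 7.3, above 480 msec, or "Change from baseline: QTcF > 60 msec"). The investigator reviews every laboratory report (Section 8.1.4), and ECGs are to be read locally (Section 8.1.3).

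**The concern.** The protocol names all three data types at the sentinel review and then sets a lower minimum at the three later ones. The core SRT recommends continuation. It could do so without knowing whether both members of the preceding pair had the same ALT, AST or QTcF shift, even though those measurements had already been scheduled.

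The setting gives this some weight. Section 4.3 acknowledges that 60 mg/kg exceeds the sponsor's own 40 mg/kg NOAEL. According to the protocol's summary of changes, Part 2 laboratory monitoring was increased after FDA feedback because no single dose above 40 mg/kg had been studied in humans. Grade 2 to 4 ALT/AST is a primary endpoint, and Section 2.3.1 lists liver chemistry elevation as a risk. Yet release of the third and fourth pairs is not tied to any of the extra laboratory results.

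**Working it through.** **1. What is scheduled before each review.** Day 1 is the infusion day, so a minimum of 4 days after infusion means 96 h, or Day 5. The Part 3 review follows discharge on Day 4. Counting post-dose entries through Day 4 in the Schedules of Activities (Sections 1.6 and 1.7), and reading the Part 2 laboratory arrow from Day 2 to Day 8 as daily:

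| | Laboratory panels per person | Triplicate ECG time points per person |
|---|---|---|
| Part 2 | 3 (Days 2, 3, 4) | 5 (end of infusion, 4 h, Days 2, 3, 4) |
| Part 3 | 3 (Days 2, 3, 4) | 4 (4 h, Days 2, 3, 4) |

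Each review covers two people:

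- Each Part 2 review: 2 x 3 = 6 panels and 2 x 5 = 10 ECG time points.
- The Part 3 review: 2 x 3 = 6 panels and 2 x 4 = 8 ECG time points.
- All three reviews: 6 + 6 + 6 = 18 panels and 10 + 10 + 8 = 28 ECG time points.

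**2. Who is dosed on these reviews.** Two pairs in Part 2 (2 + 2 = 4 of 8) and the second Part 3 cohort (6 of 8), so 10 of 16 planned participants.

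**3. Whether other provisions fill the gap.**

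- *Timing.* A pause rule acts only on a known result. No section requires results to be back before release, and no turnaround is stated. Section 8.1.4 sends tests through the central laboratory, while Section 10.2 allows central or local. In Part 3 the last draw falls on the day of discharge, and the synopsis gives no minimum interval before the review.
- *Liver.* Exclusion criterion 16 requires ALT below 1.5 x ULN at entry, and the pause starts at 3 x ULN. ALT can therefore at least double from any permitted entry value without a laboratory pause. AST has no laboratory pause limit. An AST rise could pause the study only as a related AE: one at Grade 4, or Grade 3 related AEs in two participants.
- *QTcF.* A rise of up to 60 msec does not pause the study if the value stays at or below 480 msec. The SAP's ECG section says "categories for maximum change from baseline in QTcF will include increase of" up to 30, above 30 to 60, and above 60 msec, so the middle band will be tabulated at the end but need not be seen at release.
- *AE reporting.* Under Section 10.3.1, laboratory and ECG abnormalities become AEs if "considered clinically significant in the medical and scientific judgment of the investigator". Appendix 7 also keeps subclinical sodium, potassium, chloride, bicarbonate, BUN and glucose results out of the AE data below Grade 2.

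**4. The wait if Day 4 results were required.** Turnaround T is not given, so 12, 24, 48 and 72 h from draw are assumed. In Part 2 the Day 4 draw is at 72 h (window 66 to 78 h) and the earliest review is at 96 h, so the wait is max(0, draw time + T - 96). In Part 3 it is at most T.

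| T (h) | Part 2, draw at 72 h | Part 2, draw at 78 h | Part 3, at most |
|---|---|---|---|
| 12 | 0 | 0 | 12 |
| 24 | 0 | 6 | 24 |
| 48 | 24 | 30 | 48 |
| 72 | 48 | 54 | 72 |

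**The case against.** The stated requirement is a minimum, so the core SRT may look at more. Clinically significant laboratory and ECG changes are AEs and reach the team that way. Medical monitors sit on the core SRT, and liver stopping events go to the sponsor within 24 hours. One participant crossing the ALT or QTcF limit pauses the study whatever the between-cohort review says.

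A lighter review after the sentinels is also defensible. All Part 2 pairs receive the same dose, and the sentinels have had a full review. Later pairs stay in the clinic to Day 8. Modelling in Section 4.3 puts concentrations below the average 40 mg/kg Cmax within 72 hours. The risk assessment in Section 2.3.1 names no QT hazard. The fix would also put sub-threshold values before the core SRT with no rule for acting on them.

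Most of this stands, and it limits the size of the point. The counts above measure assessments, not risk. The earlier study had 3 participants (14%) with transient Grade 1 or 2 liver enzyme rises (2 ALT, 1 AST), but their onset is not given, so they cannot be said to show by Day 4. The AST and QTcF bands illustrate what could go unseen; the point does not depend on them. What the objection does not supply is any requirement that results be back, or seen by the core SRT, before the next participants are dosed.

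**Conclusion.** The point holds as a limited gap that should be corrected. Three of the four between-cohort reviews, which release 10 of the 16 planned Part 2 and Part 3 participants, can be completed on AE data alone. Results still pending at that moment, and shifts that the investigator does not call clinically significant, can be missed by the body recommending continuation. Known breaches of the ALT and QTcF limits are already covered.

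The panel count depends on reading the Part 2 laboratory arrow as daily. The Part 3 requirement is taken from the synopsis, because the corresponding text in Section 4.1 is redacted; the Part 2 finding does not depend on it.

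**What to change.** In protocol Sections 1.1, 4.1 and 10.1.5, require every between-cohort review to cover the safety laboratory and ECG results scheduled through Day 4, confirmed as received, together with AEs. Day 4 carries the last scheduled ECG before the earliest review in both parts. Keep the existing intervals as minimums.

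The change is wording only, with no new samples, visits or procedures. The cost is a possible wait for the laboratory. At an assumed 24 h turnaround this is 0 to 6 h in Part 2 for a Day 4 draw at the nominal time or later, and at most 24 h in Part 3. At 72 h it is at most 54 h and 72 h respectively.

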4.2. Scientific Rationale for Study Design

GSK3810109 is a human MAb active against HIV that can mediate extraordinary breadth and potency against various HIV isolates, including strains traditionally resistant to other antibodies in this class.

This study is designed to evaluate safety, tolerability, and PK endpoints in healthy adult participants, when GSK3810109 is administered as either SC injection (Part 1 and Part 3 of study) or IV infusion (Part 2 of study). The inclusion of both routes of administration in this study is an efficient design to enable rapid progression to future studies using either 1 or both routes of administration.

The potency of GSK3810109 may indicate fewer antibodies are required to mediate an effect, offering the possibility of SC administration as a more feasible approach to immunoprophylaxis. The introduction of the leucine serine (LS) site-directed mutation to increase FcRn binding affinity is postulated to result in increased antibody half-life and persistence at biologically higher concentrations in the plasma, as was shown for VRC01LS and VRC07-523LS (Rudicell, 2014; Ko, 2014; Gaudinski, 2018).

The rHuPH20 enzyme facilitates SC delivery of co-administered therapeutics. The use of rHuPH20 with GSK3810109 offers the potential to administer a larger volume of the antibody than could be administered alone (~2.0 mL). Therefore, the current study will investigate the ability to deliver a larger SC dose of GSK3810109 (20 mg/kg, up to 24 mL) in combination with rHuPH20. The rHuPH20 will be co-mixed with GSK3810109 at a concentration of 2000 U/mL based on the dosing volume of GSK3810109.

In clinical studies to date for SC doses of rHuPH20 up to 30,000 U, systemic exposure has been undetectable [Kirschbrowne, 2018](#). [\[cc\]](#)

There is a practical limitation for administration of high doses of GSK3810109 via SC infusion. To date, the maximum dose administered via SC route is 20 mg/kg, in combination with rHuPH20, while an IV route allows higher dose administration. In this study, an IV dose of 60 mg/kg of GSK3810109 will be administered, which offers the potential for an ultra-long-acting target profile to support administration every 4 to 6 months, thus reducing dosing frequency and potentially improving adherence and acceptability. Medication adherence and decreasing frequency of clinic visits is the most important determinant for sustained viral suppression and long-term treatment success.

This study is participant to the appropriate regulatory and ethics committee (EC) approval and will be listed on the website ClinicalTrials.gov. No blinding or placebo control will be used, as these are not necessary for the purposes of this study.

